3.3 Exclusion Criteria

Subjects who meet any of the following criteria will be excluded from the study:

1. The subject has experienced acute pathologic fracture or spinal cord compression within 28 days prior to first dose of study therapy.
2. The subject has a known hypersensitivity to monoclonal antibodies or to agents of similar biologic composition as IMC-CS4.
3. The subject has received treatment with any monoclonal antibodies within 4 weeks prior to first dose of study therapy.
4. The subject has undergone a major surgical procedure, open biopsy, radiofrequency ablation, or has experienced a significant traumatic injury within 28 days prior to enrollment.
5. The subject has a history of another primary cancer, with the exception of a) curatively resected non-melanomatous skin cancer; b) curatively treated cervical carcinoma in situ; or c) other primary solid tumor treated with curative intent, no known active disease present, and no treatment administered during the last 3 years prior to study entry.
6. The subject is receiving concurrent treatment with other anticancer therapy, including other chemotherapy, immunotherapy, chemoembolization, targeted therapy, or any investigational agent within 4 weeks prior to study entry, or radiotherapy within 2 weeks prior to study entry. An exception is that subjects with metastatic breast or prostate cancer who have been on a stable dose (≥ 28 days) of an approved hormonal agent will not be excluded (ie, they will be eligible). Subjects with breast cancer may also continue with concurrent human epidermal growth factor receptor 2 (HER2)-directed therapy.
7. The subject has known muscle damage due to a primary, traumatic, or other muscle disease.
8. The subject is known to be human immunodeficiency virus (HIV) seropositive.
9. The subject has a known and uncontrolled infection.
10. The subject is known to have active tuberculosis, leishmaniasis, or listeriosis.
11. The subject has a history of and/or current: symptomatic coronary artery disease, confirmed left ventricular ejection fraction (LVEF) $\leq 50\%$ or any cardiac insufficiency $>$ New York Heart Association (NYHA) class II,* uncontrolled hypertension, or serious cardiac arrhythmia (well-controlled atrial fibrillation is permitted).
12. Subjects with known history, or clinical or laboratory evidence of, liver disease. Notably, subjects with any of the following liver function abnormalities will be excluded:
 - a Cirrhosis with evidence of portal hypertension or bridging fibrosis
 - b Alcoholic hepatitis
 - c Esophageal varices
 - d A history of bleeding esophageal varices
 - e Hepatic encephalopathy
 - f Ascites related to portal hypertension

- g Chronic viral hepatitis with total serum bilirubin >3 mg/dL.
- 13. The subject has active bleeding.
- 14. The subject has leukemia or lymphoma.
- 15. The subject has a known psychiatric illness/social situation (including alcohol and/or drug dependency) that, in the Investigator's opinion, would limit compliance with study requirements.
- 16. The subject has known or suspected primary brain or leptomeningeal tumors or metastases (subjects with a history of brain metastases must have received definitive surgery or radiotherapy, be clinically stable, and may not be taking steroids; subjects receiving anticonvulsants are eligible).
- 17. The subject is pregnant (confirmed by serum beta human chorionic gonadotropin [β -hCG] test performed within 7 days prior to first dose of study therapy) or breastfeeding.
- 18. The subject has received a solid organ transplant.
- 19. The subject has any other serious uncontrolled medical disorders that, in the opinion of the Investigator, would compromise the subject's safety or the ability of the subject to participate in the study.

*NYHA Congestive Heart Failure Classification (NYHA 1994):

Class I – Patients with no limitation of activities; they suffer no symptoms from ordinary activities.

Class II – Patients with slight, mild limitation of activity; they are comfortable with rest or with mild exertion.

Class III – Patients with marked limitation of activity; they are comfortable only at rest.

Class IV – Patients who should be at complete rest, confined to bed or chair; any physical activity brings on discomfort and symptoms occur at rest.

Throughout this protocol, "days" refers to calendar days, unless otherwise indicated.

3.4 Subject Enrollment

All subjects meeting the eligibility requirements will be considered for enrollment regardless of race, religion, or sex. Subjects will be recruited from a population of subjects with advanced solid tumors who have been previously evaluated at the participating institution or have been referred from other institutions. The Investigator will review the subject's medical record to determine his or her eligibility for the study. The criteria for enrollment must be followed explicitly. Exceptions to the eligibility criteria may not be granted by the Investigator or the Sponsor. If a subject who does not meet enrollment criteria is unintentionally enrolled, the Investigator informs the subject of the inadvertent enrollment, and the Sponsor or its designee must be contacted. In these rare cases, the Investigator must obtain documented approval from the Sponsor to allow the subject to continue in the study.

Subjects will be made aware of the protocol, its specific aims and objectives, and the potential risks and benefits the subject may incur. Each subject will be required to read, agree to, and sign a current Institutional Review Board (IRB)/approving Ethics Committee (aEC)-approved ICF prior to being enrolled and before any study-related procedure is performed. There will be no financial compensation for subjects enrolling on this protocol.

Individuals who do not meet the criteria for participation in this study (screen failure) within 14 days after study entry may be rescreened once. Sites are responsible for determining if the subject must sign a new ICF, based on regulatory and institutional or central IRB/aEC guidelines. All subjects who have signed an informed consent form will be assigned a study identification (ID) number.

Screening and other pretreatment evaluations will be performed as described in Section [7.1](#).

3.5 Method of Assigning Subjects to Treatment

Sites will enroll subjects into the study via facsimile and/or e-mail to the Sponsor. Each subject will be assigned a unique study ID number. The study ID number is to be recorded on all electronic case report forms (eCRFs) and correspondence regarding the subject, and will be used in lieu of the subject's name to protect the subject's identity when reporting AEs and/or other study-related data. Once the study ID number is obtained, the Investigator must administer the first dose of investigational agent to the subject within 7 days. Specific instructions regarding the enrollment and registration process will be provided in a separate procedure manual.

3.6 Blinding

This is an open-label Phase 1 dose-escalation study; no blinding will be utilized.

4 INVESTIGATIONAL PLAN

4.1 Overall Study Design and Plan

This open-label, dose-escalation, Phase 1 study will enroll a total of approximately 72 subjects to 2 parts - Parts A and B, in approximately 6 study sites in the United States. Part A consists of dose escalation of IMC-CS4 using weight-based dosing (Part A enrollment is planned to be discontinued as of 30 September 2015); Part B will consist of dose escalation of IMC-CS4 using non-weight-based dosing; the actual enrollment will depend on the number of DLTs observed and the resultant size of each cohort. Throughout this protocol, any information not indicated as “Part A only” or “Part B only” is relevant to both parts. In Part A, additional subjects were enrolled to the maximum tolerated dose (MTD) of 1.25 mg/kg q2w, in order to help establish the safety profile of IMC-CS4. In Part B, the cohort associated with the dose identified as the MTD may be expanded (up to a maximum of 12 evaluable subjects) in order to help establish the safety profile of IMC-CS4. Enrollment to the MTD expansion cohort may cease if the Sponsor (after conferring with the investigators) deems the toxicity profile precludes further enrollment. Refer also to Section [4.1.2](#).

Dose cohorts, including dose and dosing schedule, are summarized in [Table 1](#). For each cohort, one cycle is 6 weeks. In each cohort, subjects will receive IMC-CS4 by I.V. infusion (with an observation period, in Part A only, for weekly [qw] and every-2-week [q2w] cohorts, in Cycle 1 only, as described in [Table 1](#)). Beginning with Protocol Amendment Version 7.0, enrollment to Part B of the study will start with Cohort 6a, then escalate to Cohorts 7a and 8a. In the event 2 or more subjects on Cohort 6a experience a DLT event, concurrent enrollment of 3 to 6 subjects to each of Cohorts 6b and 6c will start and further dose escalation (that is, to Cohort 7a) will cease. Likewise, the same algorithm will apply for Cohorts 7a and 8a if enrollment to those cohorts occurs. Subjects will be assigned to “b” and “c” cohorts by the Sponsor. Note that there will be no Cycle 1 observation period for Part B cohorts. No intra-subject dose-escalation is permitted for any subject. Dose escalation may be reduced or ceased at any time based on safety and PK behavior.

Table 1. Dose Cohort Assignment

Cohort	Dose Level	Dosing Schedule^a	Cycle 1 Observation Period^b	Number of Infusions
Part A (weight-based dosing)				
1	2.5 mg/kg	qw	2 weeks (Weeks 5-6)	Cycle 1: 4 Subsequent cycles: 6
2	0.3 mg/kg	qw	2 weeks (Weeks 5-6)	Cycle 1: 4 Subsequent cycles: 6
3	0.6 mg/kg	qw	2 weeks (Weeks 5-6)	Cycle 1: 4 Subsequent cycles: 6
4	1.25 mg/kg	q2w	3 weeks (Weeks 4-6)	Cycle 1: 2 Subsequent cycles: 3
5	1.25 mg/kg	qw	2 weeks (Weeks 5-6)	Cycle 1: 4 Subsequent cycles: 6
Part B (non-weight-based dosing)				
6a	100 mg	qw	None	Cycle 1: 6 Subsequent cycles: 6
6b ^{c,d}	100 mg	qw on Weeks 1, 2, 4, and 5	None (Weeks 3 and 6 are rest)	Cycle 1: 4 Subsequent cycles: 4
6c ^c	75 mg	qw	None	Cycle 1: 6 Subsequent cycles: 6
7a	150 mg	qw	None	Cycle 1: 6 Subsequent cycles: 6
7b ^{c,d}	150 mg	qw on Weeks 1, 2, 4, and 5	None (Weeks 3 and 6 are rest)	Cycle 1: 4 Subsequent cycles: 4
7c ^c	125 mg	qw	None	Cycle 1: 6 Subsequent cycles: 6
8a	200 mg	qw	None	Cycle 1: 6 Subsequent cycles: 6
8b ^{c,d}	200 mg	qw on Weeks 1, 2, 4, and 5	None (Weeks 3 and 6 are rest)	Cycle 1: 4 Subsequent cycles: 4
8c ^c	175 mg	qw	None	Cycle 1: 6 Subsequent cycles: 6

Abbreviations: aEC = approving Ethics Committee; DLT = dose-limiting toxicity;

IRB = Institutional Review Board; PK = pharmacokinetic(s); qw = weekly; q2w = every 2 weeks.

a – At the highest dose level where major toxicity is observed and that requires a longer recovery period between infusions, a change in the periodicity of dosing (that is, other dosing schedules based on safety and PK considerations) will be agreed upon with the Investigator and communicated to IRBs/aECs.

b – Observation following the fourth infusion in Cohorts 1, 2, 3, and 5 (qw dosing) and the second infusion in Cohort 4 (q2w dosing) in Cycle 1 only. No Cycle 1 observation period for Cohorts 6a, 6c, 7a, 7c, 8a, or 8c. Weeks 3 and 6 of all cycles are rest weeks in Cohorts 6b, 7b, and 8b (qw dosing on Weeks 1, 2, 4, and 5).

c – Concurrently enroll to Cohorts 6b/7b/8b and 6c/7c/8c, should ≥ 2 subjects in Cohort 6a/7a/8a experience DLT events.

d – For all cycles: Infusions on Weeks 1, 2, 4, and 5, and rest on Weeks 3 and 6.

It is recognized that in the course of clinical cancer care, it is not always possible to schedule therapeutic infusions at precise intervals (because of holidays, travel difficulties, or other circumstances). Accordingly, infusions administered within 2 days (all cohorts other than q2w

dosing) or 3 days (q2w dosing) before or after the planned infusion time point will be considered acceptable. Deviations beyond this window are not permitted in Cycle 1 and will be allowed thereafter only if medically indicated or if the subject cannot be treated on the scheduled day.

Following the first cycle of therapy (Cycle 1), subjects should continue to receive IMC-CS4 at the same dose and schedule until there is unequivocal evidence of disease progression (per immune-related response criteria [Wolchok et al. 2009]) or other withdrawal criteria are met. Radiographically confirmed disease progression (that is, numerical disease progression, per RECIST) only is not sufficient to discontinue treatment.* Radiographic assessment of tumor response will be performed at the end of the initial 6-week cycle and at the end of every subsequent cycle; radiographic assessment should be performed prior to the start of a cycle so that results are available before the subject receives a new cycle of treatment. However, if a DLT is observed in Cycle 1 in a subject who is benefitting from treatment, Cycle 2 dosing may be initiated within 4 weeks of Cycle 1, Day 1, with Sponsor approval; in this case, no radiographic disease assessment is required prior to dosing in Cycle 2.

*Note: Subjects with disease progression (per RECIST) but without clinical deterioration at Week 6 (the first response assessment) may continue to receive IMC-CS4, at the discretion of the Investigator; study treatment will be discontinued if, at the next disease assessment (performed at least 4 weeks later), disease progression is unequivocal (that is, radiographically confirmed disease progression alone is sufficient). On the other hand, subjects with disease progression (per RECIST) and with clinical deterioration (unequivocal) at Week 6 (the first response assessment) will be discontinued from study treatment.

The treatment schedule, radiographic tumor assessment schedule, and observation period for each dosing schedule are summarized in [Table 2](#), [Table 3](#), [Table 4](#), and [Table 5](#).

Table 2. Treatment Schedule (Part A - Weekly Dosing – Cohorts 1, 2, 3, and 5)

Week	1	2	3	4	5	6	7	8	9	10	11	12	13	14	15	16	17	18	19	20	21	22	23	24
	Cycle 1						Cycle 2						Cycle 3						Cycle 4					
Tx ^a	X	X	X	X			X	X	X	X	X	X	X	X	X	X	X	X	X	X	X	X	X	X
O.P. ^b					X	X																		
Tumor eval ^c	X ^d				X						X						X							X

Abbreviations: eval = evaluation; O.P. = observation period; Tx = treatment.

a – Administer IMC-CS4; b – Observation period; c – Radiographic assessment of tumor status; d – Baseline assessment, within 28 days prior to the first dose of study therapy; subsequent assessment should be performed in the week prior to the onset of the new cycle.

Table 3. Treatment Schedule (Part A - Every-2-Week Dosing – Cohort 4)

Week	1	2	3	4	5	6	7	8	9	10	11	12	13	14	15	16	17	18	19	20	21	22	23	24
	Cycle 1						Cycle 2						Cycle 3						Cycle 4					
Tx ^a	X		X				X		X		X		X		X		X		X		X		X	
O.P. ^b				X	X	X																		
Tumor eval ^c	X ^d				X					X							X							X

Abbreviations: eval = evaluation; O.P. = observation period; Tx = treatment.

a – Administer IMC-CS4; b – Observation period; c – Radiographic assessment of tumor status; d – Baseline assessment, within 28 days prior to the first dose of study therapy; subsequent assessment should be performed in the week prior to the onset of the new cycle.

Table 4. Treatment Schedule (Part B - Weekly Dosing – Cohorts 6a, 6c, 7a, 7c, 8a, and 8c)

Week	1	2	3	4	5	6	7	8	9	10	11	12	13	14	15	16	17	18	19	20	21	22	23	24
	Cycle 1						Cycle 2						Cycle 3						Cycle 4					
Tx ^a	X	X	X	X	X	X	X	X	X	X	X	X	X	X	X	X	X	X	X	X	X	X	X	X
O.P. ^b																								
Tumor eval ^c	X ^d					X					X						X							X

Abbreviations: eval = evaluation; O.P. = observation period; Tx = treatment.

a – Administer IMC-CS4; b – Observation period; c – Radiographic assessment of tumor status; d – Baseline assessment, within 28 days prior to the first dose of study therapy; subsequent assessment should be performed in the week prior to the onset of the new cycle.

Table 5. Treatment Schedule (Part B - Weekly Dosing on Weeks 1, 2, 4, and 5 – Cohorts 6b, 7b, and 8b)

Week	1	2	3	4	5	6	7	8	9	10	11	12	13	14	15	16	17	18	19	20	21	22	23	24
	Cycle 1						Cycle 2						Cycle 3						Cycle 4					
Tx ^a	X	X		X	X		X	X		X	X		X	X		X	X		X	X		X	X	
O.P. ^b																								
Tumor eval ^c	X ^d					X					X						X							X

Abbreviations: eval = evaluation; O.P. = observation period; Tx = treatment.

a – Administer IMC-CS4; b – Observation period; c – Radiographic assessment of tumor status; d – Baseline assessment, within 28 days prior to the first dose of study therapy; subsequent assessment to be performed in the week prior to the onset of the new cycle.

4.1.1 Cohort Enrollment and Dose Escalation

Each cohort will initially enroll at least 3 subjects. In the first cohort (Cohort 1), subjects were to be enrolled sequentially. That is, there was to be a minimum of a 7-day waiting period between the time a subject receives the first dose of IMC-CS4 and when the next subject in Cohort 1 receives his or her first dose.

For all subsequent cohorts, no 7-day waiting period is required.

Beginning with Cohort 2 and provided safety is acceptable, concomitant enrollment of subjects at different sites will be permitted, in order to ensure that at least 3 subjects will be treated for at least 1 cycle. In a case where consent is obtained simultaneously for 2 subjects at 2 different sites, this may result in enrollment of 4 subjects rather than 3 in a cohort; however, no more than 4 subjects should be enrolled in a cohort before safety data from Cycle 1 are available for review.

For all cohorts, all subjects who complete the first treatment cycle (that is, receive all scheduled treatments for Cycle 1 and complete the observation period, as needed) or discontinue therapy due to a DLT will be considered evaluable subjects and will be included in the DLT analyses. Subjects who do not complete Cycle 1 for reasons other than a DLT will be replaced for the analysis until the cohort includes 3 evaluable subjects (or 6 evaluable subjects in case of one DLT in the first 3 subjects); however, if benefitting from treatment (that is, no disease progression or other withdrawal criteria), any subject in Cohort 3 and beyond who experiences a DLT may continue to receive IMC-CS4 upon agreement of the Sponsor and according to the dose reduction guidelines for this study. Refer to Section 10.1 for details of general dose modifications for IMC-CS4.

If the first 3 subjects in a cohort complete Cycle 1 of therapy with no DLT (defined in Section 4.1.4), dose escalation to the next cohort may proceed. If one of the first 3 subjects in a cohort experiences a DLT, enrollment will proceed until there are at least 6 evaluable subjects in that cohort. If no additional subject experiences a DLT, dose escalation may proceed. If 2 or more subjects experience a DLT in a cohort (whether in the initial 3-subject cohort or following expansion to 6 subjects), dose escalation will not occur and the RP2D will be determined according to the instructions in Section 4.1.2.

In all cases, dose escalation will occur only if the criteria described in this section (Section 4.1.1) are met. Each subsequent cohort will be opened upon completion of the previous cohort. A safety review meeting will be held prior to each dose escalation.

4.1.2 Determination of the Recommended Dose for Phase 2

The provisional RP2D will be defined as the dose level at which pharmacodynamic effects are observed in the absence of clinically relevant toxic effects (that is, measurable pharmacodynamic effects with no DLT in the first 3 subjects or ≤ 1 DLT in the first 6 subjects enrolled at that dose level). After discussion with the Investigator, the Sponsor may choose to enroll additional subjects at or below the RP2D.

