10 DOSE MODIFICATIONS

10.1 General Dose Modifications – IMC-CS4

10.1.1 During Cycle 1

No IMC-CS4 dose reductions were permitted for any subject (in Cohort 1 or 2) following a DLT. If a subject (in Cohort 1 or 2) experienced a DLT during Cycle 1, IMC-CS4 was permanently discontinued.

If benefitting from treatment (that is, no disease progression or other withdrawal criteria), any subject in Cohort 3 and beyond who experiences a DLT may continue to receive IMC-CS4 upon agreement of the Sponsor and according to the dose reduction guidelines for this study ([Table 12](#)).

In the setting of non-life-threatening reversible Grade ≤ 3 IMC-CS4-related toxicities in Cycle 1 that do not meet the definition of a DLT, IMC-CS4 may be held (if appropriate, in the opinion of the Investigator and upon agreement with the Sponsor) for a maximum of 3 weeks, until resolution to baseline or improvement to Grade ≤ 2 . Upon resolution to baseline or improvement to Grade ≤ 2 , IMC-CS4 may be administered at a reduced dose (according to [Table 12](#)) beginning with Cycle 2, if appropriate, in the opinion of the Investigator and upon agreement with the Sponsor (no dose reductions are permitted during Cycle 1 [for subjects in Cohort 1 or 2]; subjects [in Cohort 1 or 2] who would require dose reductions during Cycle 1 must be discontinued). If toxicity does not resolve to baseline or improve to Grade ≤ 2 within 3 weeks following the last administered dose, IMC-CS4 should be permanently discontinued.

10.1.2 After Cycle 1

Dose reductions, if required during Cycle 2 or after, in the context of IMC-CS4-related toxicity, may be implemented according to the guidelines in [Table 12](#). Any individual subject (including those experiencing an event that occurred after the DLT assessment period that otherwise would have been considered a DLT) may be dose reduced a maximum of 2 times during the course of the study (except as noted in [Table 12](#); for example, subjects in Cohort 3 are only permitted to have one dose reduction). Once a subject has had a dose reduction (has started a new cycle at the reduced dose), all subsequent infusions will be at the reduced dose level; there will be no

resumption to prior dose level(s). Any subject experiencing toxicity that would necessitate more than 2 dose reductions must discontinue treatment. Dose reductions must be confirmed by the Sponsor.

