10.2 Removal of Subjects from Therapy

The Investigator must withdraw a subject from IMC-CS4 for any of the following reasons:

- The Sponsor or Investigator terminates the study;
- The Investigator/physician or Sponsor decides that the subject should be withdrawn from the study or study drug;
- The subject, for any reason, requires treatment with another therapeutic agent that has been demonstrated to be effective for treatment of the study indication (discontinuation from the study drug to occur prior to introduction of the other agent);
- An unacceptable AE/toxicity (for example, a persistent moderate toxicity that is intolerable to the subject or requires >2 dose reductions);
- A DLT occurring in a subject in Cohort 1 or 2 only (a DLT occurring in a subject in Cohort 3 or beyond would not necessarily be a withdrawal criterion);
- A Grade 3-4 infusion-related reaction;
- Any therapy-related event that is deemed life-threatening, regardless of NCI-CTCAE, Version 4.0 grade;
- Any event that would warrant IMC-CS4 therapy to be held for more than 3 weeks following the last administered dose, or to be dose reduced more than 2 times;
- Radiographic documentation of PD (refer to Note in Section 4.1);
- A decline in ECOG PS that, in the opinion of the Investigator, necessitates discontinuation of study therapy;
- Subject noncompliance (in the opinion of the Investigator or Sponsor) with this study protocol;
- Subject pregnancy or breastfeeding;
- Enrollment by the subject in any other clinical trial involving an investigational product or enrollment in any other type of medical research judged not to be scientifically or medically compatible with this study;
- An intercurrent illness or change in the subject's condition that renders the subject unsuitable for further treatment in the opinion of the Investigator and/or Sponsor; and/or
- Withdrawal of consent.

After termination of study therapy, the subject will be treated as clinically indicated by the Investigator or referring physician. If the reason for withdrawal from the trial is the death of the subject, the 2 options for categorizing withdrawal are either: (1) PD or (2) an AE (more than one

AE may be documented as a reason for withdrawal). Only one event will be recognized as the cause of death.

If a subject is discontinued from all study therapy:

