12.2 Analysis Populations

All enrolled subjects who received at least one dose of IMC-CS4 will be included in the safety population.

Subjects who complete the initial 6 weeks of therapy (that is, receive all scheduled treatments for Cycle 1 and complete the observation period, as needed) or experience a DLT will be included in the DLT population. The DLT population will be used for the determination of the RP2D, including evaluation of DLTs. All other variables (including demographic and baseline subject characteristics, efficacy and safety variables) will be analyzed using the safety population.

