5.1.2 Safety Population

All enrolled subjects who received at least one dose of IMC-CS4 will be included in the Safety Population, regardless of their eligibility for the study. The Safety population will be used for the analysis of baseline characteristics, efficacy data and safety data.

5.1.3 ~~Maximum Tolerated Dose~~Dose Limiting Toxicity

~~(MTD-DLT)~~ Population

Subjects who complete the initial 6 weeks of therapy¹ or experience a DLT during the first cycle will be included in the ~~MTD-DLT~~ Population. Patients who discontinued during the initial 6 weeks due to reasons other than DLT will be excluded from the ~~MTD-DLT~~ population. The ~~MTD-DLT~~ population will be used for the evaluation of DLTs in order to determine the ~~MTDRP2D~~.

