5.3.4 Analyses of Safety Data

5.3.4.1 Study Drug Exposure

The following variables will be summarized according to the definitions provided in section 5.2.1.4. Exposure analyses will include the following:

Cycle 1 only using the MTD population:

- Number of infusions
- Cumulative dose (mg/kg)
- Dose intensity (mg/kg/week)
- ~~Adjusted dose intensity (mg/kg/week)~~
- Relative dose intensity (%)
- Number (%) of subjects with dose modifications (reduced or change of infusion rate).

Across all cycles using the Safety population

- Duration of treatment (weeks)
- Duration of cycles (weeks)
- Number (%) of subjects treated by cycle.
- Number of infusions
- Cumulative dose (mg/kg)
- Dose intensity (mg/kg/week)
- Adjusted dose intensity (mg/kg/week)
- Relative dose intensity (%)
- Number (%) of subjects with dose modifications (reduced or change of infusion rate).

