5.3.4.3 Treatment Emergent Adverse events

Treatment-emergent AEs will be summarized by MedDRA® System Organ Class (SOC) and preferred term (PT), classified from verbatim terms. The incidence and percentage of subjects with at least one occurrence of a preferred term will be included, according to the most severe NCI-CTCAE grade. Causality (relationship to study drug) will be summarized separately. If more than one AE is recorded for a patient within any SOC or PT term, the patient will only be counted once on the most severe grade and the closest relationship to treatment.

AEs reported with a causal relationship of ‘possibly related’ and ‘probably related’ to study medication or ‘does not know’ will be considered related to study medication. Missing classifications concerning study medication relationship will be considered as related to study medication.

The following will be summarized using the Safety population for all AEs, and the MTD population for AEs with onset date in Cycle 1 (ie, within 21 days after last dose in Cycle 1 and prior to start of Cycle 2):

- All AEs,
- SAEs,
- NCI-CTCAE Grade 3 or higher AEs,
- Related AEs, SAEs, and NCI-CTCAE Grade 3 or higher AEs,
- AEs leading to dose modification, study medication discontinuation, and death will be summarized according to MedDRA® Preferred Terms.
- Duration of AE will be determined and included in listings along with action taken and outcome.

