6.3 Planned Safety Tables

Table Number	Table Title	Population
	Dose Exposure	
14.3.1.1	IMC-CS4 Dose Exposure in Cycle 1	DLT
14.3.1.2	IMC-CS4 Dose Exposure	Safety
14.3.2	IMC-CS4 Dose Delays and Modifications in Cycle 1	DLT
14.3.2	IMC-CS4 Dose Delays and Modifications	Safety
	Adverse events	
14.3.5	Summary of Adverse Events	Safety
14.3.6	DLTs by SOC and PT (Cycle 1)	DLT
14.3.7.1	Adverse Events by SOC and PT	Safety
14.3.7.2	Adverse Events by SOC and PT (Cycle 1)	DLT
14.3.8.1	Severe Adverse Events by SOC and PT	Safety
14.3.8.2	Severe Adverse Events by SOC and PT (Cycle 1)	DLT
14.3.9.1	Serious Adverse Events by SOC and PT	Safety
14.3.9.2	Serious Adverse Events by SOC and PT (Cycle 1)	DLT
14.3.10.1	Related Adverse Events by SOC and PT	Safety
14.3.10.2	Related Adverse Events by SOC and PT (Cycle 1)	DLT
14.3.11.1	Related Severe Adverse Events by SOC and PT	Safety
14.3.11.2	Related Severe Adverse Events by SOC and PT (Cycle 1)	DLT
14.3.12.1	Related Serious Adverse Events by SOC and PT	Safety
14.3.12.2	Related Serious Adverse Events by SOC and PT (Cycle 1)	DLT
14.3.13.1	Adverse Events Resulting in Treatment Delay or Modifications by SOC and PT	Safety
14.3.13.2	Adverse Events Resulting in Treatment Delay or Modifications by SOC and PT (Cycle 1)	DLT

14.3.14.1	Adverse Events Resulting in Treatment Discontinuation by SOC and PT	Safety
14.3.14.2	Adverse Events Resulting in Treatment Discontinuation by SOC and PT (Cycle 1)	DLT
14.3.15.1	Adverse Events Resulting in Death by SOC and PT	Safety
14.3.15.2	Adverse Events Resulting in Death by SOC and PT (Cycle 1)	DLT
14.3.16.1	Adverse Events by SOC and PT and Worst Grade	Safety
14.3.16.2	Adverse Events by SOC and PT and Worst Grade (Cycle 1)	DLT
14.3.17	Deaths	Safety
	Physical Examination, Vital Signs, Laboratory Assessments, ECG	
14.3.18	Physical Examination Abnormalities by Scheduled Time	Safety
14.3.19	ECOG Performance Status Shift Table	Safety
14.3.20.3	Vital Signs Shift from Pretreatment to End-of-Study	Safety
14.3.21.1	Vital Signs Shift from Preinfusion to Highest-on-Infusion	Safety
14.3.21.2	Vital Signs Shift from Preinfusion to Lowest-on-Infusion	Safety
14.3.21.3	Vital Signs Shift from Preinfusion to End-of-Infusion	Safety
14.3.22.1	Laboratory CTC Grade Shift from Baseline to Worst Post Baseline Grade- Tests Graded in Single Direction(Either Above or Below Normal Range)	Safety

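### The SAP runs its Cycle 1 exposure, adverse-event and discontinuation tables on the DLT population, which leaves out subjects who stopped Cycle 1 for a non-DLT event

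*Protocol*

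**What the plan says.** **Protocol.** Section 4.1.1 makes a subject evaluable in one of two ways: finishing Cycle 1, or discontinuing because of a DLT. Of everyone else it says "Subjects who do not complete Cycle 1 for reasons other than a DLT will be replaced for the analysis". Section 12.2 defines finishing as to "receive all scheduled treatments for Cycle 1 and complete the observation period, as needed", and admits to the DLT population any subject who has a DLT. It assigns that population to DLT evaluation and RP2D determination, and all other variables to the Safety population (everyone dosed at least once). Section 12.5.2 repeats the split: DLT counts on the DLT population, all other safety analyses on the Safety population.

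**SAP.** Section 5.1.2 gives the Safety population the baseline, efficacy and safety analyses. Section 5.1.3 defines the DLT population, formerly called the MTD population, and states its purpose as evaluating DLTs to set the RP2D: "Patients who discontinued during the initial 6 weeks due to reasons other than DLT will be excluded". The analysis sections then use it more widely. Section 5.3.4.1 plans exposure summaries for "Cycle 1 only using the MTD population". Section 5.3.4.3 uses "the MTD population for AEs with onset date in Cycle 1". The table list in 6.3 carries this through under the new name, DLT.

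**The concern.** The DLT population is built for one question: how many subjects with an adequate Cycle 1 had a DLT. For that purpose, dropping subjects who left early for other reasons is deliberate. Cycle 1 tolerability is a different question, and leaving early is part of its answer. A discontinuation table whose population is chosen by not having discontinued, except for a DLT, cannot answer it.

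At stake is the report's picture of the first six weeks. A reader comparing cohorts on Cycle 1 AEs, dose modifications or stops would see only subjects who finished the cycle or had a DLT. Establishing the safety profile is a primary objective.

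**Working it through.** No figure in the plan has to be reproduced here; the check is by definitions.

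**1. Who is in the population.** Split the treated subjects of a cohort into *c* who finish Cycle 1 without a DLT, *d* with a DLT, *k* who stop in Cycle 1 for an AE that is not a DLT, and *u* who stop for other reasons. Then:
- Safety population = *c* + *d* + *k* + *u*
- DLT population = *c* + *d*

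**2. Who can appear in Table 14.3.14.2.** Only subjects with a DLT, and finishers whose Cycle 1 AE led to a stop afterwards. The *k* subjects, who are what the table is about, add nothing to the numerator or the denominator, however many there are.

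**3. Can *k* be above zero?** Yes.
- Protocol 4.1.4 requires a DLT to be related to IMC-CS4. The discontinuation table is not limited to related AEs, so any unrelated AE that ends treatment in Cycle 1 falls in *k*.
- Related events can fall there too. Section 10.2 requires withdrawal for unacceptable toxicity, for example "a persistent moderate toxicity that is intolerable to the subject", whereas the listed DLTs are Grade 3 or 4 (reading moderate as below Grade 3).
- A Grade 3 infusion reaction forces permanent discontinuation (10.1.3), but may fall outside 4.1.4 if it improves to Grade 2 or lower within 7 days.
- The permanent stop in 10.1.1 adds little. A toxicity still above Grade 2 after 3 weeks has already failed the 7-day test, unless 4.1.4 leaves that event outside the definition.

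**4. Effect on the numbers.** Illustration with the plan's cohort sizes and an assumed *k* = 1, *u* = 0:
- 3 evaluable subjects, no DLT: the table shows 0/3 stopped; the Safety population gives 1/(3 + 1) = 1/4 = 25%.
- 6 evaluable subjects, one stopped by a DLT: the table shows 1/6 = 17%; the Safety population gives (1 + 1)/(6 + 1) = 2/7 = 29%.

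These show direction only. The documents give no value of *k*.

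**5. Exposure.** The footnote to SAP 5.1.3 defines completion by the first four infusions plus observation or entry into Cycle 2. In a weekly Part A cohort, every subject without a DLT in Table 14.3.1.1 therefore has the full four Cycle 1 infusions by selection.

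**6. How many tables.** SAP 6.3 puts 13 tables on the DLT population. One, 14.3.6 (DLTs), belongs there. The other 12 are Cycle 1 exposure, Cycle 1 delays and modifications, and ten Cycle 1 AE tables (14.3.7.2 to 14.3.16.2).

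**7. Consistency.** Those 12 uses conflict with protocol 12.2 and 12.5.2. They also go beyond the purpose that SAP 5.1.3 itself states, and against the role that SAP 5.1.2 gives the Safety population.

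**8. A related mismatch in the protocol.** Section 4.1.1 and the synopsis design text require discontinuation because of a DLT; 12.2 and the synopsis statistics text require only having one. From Cohort 3 on, a subject may continue after a DLT, and 4.1 allows Cycle 2 to begin within 4 weeks of Cycle 1 Day 1. In Cohort 6a, with six scheduled Cycle 1 infusions, such a subject has neither finished Cycle 1 nor discontinued. Read literally, 4.1.1 makes that subject not evaluable, while 12.2 includes the subject.

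**The case against.** **These subjects are not hidden.** True. Each of the 12 tables has an all-cycle counterpart on the Safety population (for example 14.3.14.1), and Listing 15.5 shows AE discontinuations by subject. Protocol 4.1.1 and 12.8 require a safety review before each escalation, covering all safety data. This limits the consequence but does not correct the Cycle 1 tables.

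**The SAP is out of date.** It was written to protocol Version 3.0 and has no Part B cohorts; the protocol is now Version 7.0. The Version 3.0 text is not available here, so the conflict is shown only against the current protocol. The tension inside the SAP, between 5.1.2 and 5.1.3 on one side and 5.3.4 and 6.3 on the other, does not depend on version.

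**A stronger reading: the replacement rule itself is faulty and eases escalation.** A reader might infer this, because a subject stopped by the drug below the DLT threshold carries no weight in the 3+3 count. The documents do not support it. Replacing such subjects is usual in a 3+3 design, and it slightly raises the DLT proportion among those counted. With an assumed 10% DLT rate and 10% non-DLT stops, that proportion is *p* = 0.10/(1 − 0.10) = 0.111, and the chance of passing is (1 − *p*)³ + 3*p*(1 − *p*)⁵ = 0.887. Keeping the same subjects as non-events (*p* = 0.10) gives 0.906. Passing becomes much less likely only if such stops are counted as toxicity, and the protocol does not define them so. Passing 3+3 also only permits escalation, which 4.1 allows to be reduced or ceased at any time.

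**Conclusion.** The Cycle 1 outputs are wrong as written. Twelve planned tables use a population that excludes, by definition, anyone who stopped in the first 6 weeks for a reason other than a DLT. Table 14.3.14.2 cannot do its job on that population, and the Cycle 1 exposure and AE summaries are conditioned on finishing the cycle or having a DLT. This follows from the definitions and needs no assumed rate; how many subjects are lost cannot be stated from the documents.

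The conclusion is confined to reporting. It does not show a biased DLT rate, an unsafe escalation rule or a need to limit replacement.

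The mismatch between 4.1.1 and 12.2 is a smaller wording matter. One might infer that a DLT could drop out of the escalation decision, but the escalation paragraph of 4.1.1 counts subjects who experience a DLT, so the intent is clear enough.

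**What to change.** - **SAP 5.3.4.1, 5.3.4.3 and 6.3:** present the Cycle 1 exposure, dose-modification, AE and discontinuation tables on the Safety population. Keep the DLT population for DLT counts and RP2D determination only. Use one name for it throughout; 5.3.4 still says MTD. Make the change when the SAP is brought into line with Version 7.0.
- **Protocol 4.1.1 and synopsis:** reconcile the wording with 12.2, so that it is clear whether a subject who has a DLT and continues treatment is evaluable.
- **Optional:** at the existing pre-escalation review, list by cohort the subjects who did not complete Cycle 1 because of an IMC-CS4-related AE that was not a DLT.

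The replacement rule, the 3+3 count and the DLT definition can stay as they are. The cost is a changed population label, a rerun of tables already planned, and a short wording edit. No new data are needed.
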